### 3.2.6 Monthly time intervals

In terms of the analysis, a month is defined as 30 days and time intervals based on monthly durations are defined as a multiple of 30 days (eg, 12 months is defined as 360 days). The following definitions of 3-month intervals are based on 30-day months where the date of first dose of BRV is Day 1:

Interval	Duration Definition
3-month interval	
Month 1-3	Day 1-90
Month 4-6	Day 91-180
Month 7-9	Day 181-270
Month 10-12	Day 271-360

Subsequent 3-month intervals are defined in a similar manner. Three-month intervals will be used for analyses of efficacy (except for continuously seizure-free) and TEAE summaries.

For the analysis of efficacy outcomes, a subject is included in the analysis of a 3-month interval if the last dose of study drug during the Evaluation Period of EP0085 is equal or

greater than the last day of the 3-month time interval and the seizure diary was completed for at least 1 day during the 3-month interval over the Evaluation Period.

For TEAE summaries, a subject is included in the analysis of a 3-month interval if the last dose of study drug in whole period of EP0085 is equal or greater than the first day of the 3-month time interval (as N for the time interval) and with at least one specified TEAE within the 3-month interval (as n in the summary tables according to the AE onset date).

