## **4 STATISTICAL/ANALYTICAL ISSUES**

### **4.1 Handling of missing data**

No rule for handling of missing data will be applied for this LTFU study. Safety and efficacy variables will be analyzed as available. Days with missing information will be ignored in the calculation of the seizure frequency.

Since subjects may drop out from the study at different times, selected summaries will be presented by time interval.

Subjects participating in EP0118 while also enrolled in EP0085 will have missing data for seizure frequency and drug dosing while participating in the EP0118 study. As the duration of the EP0118 study will be short (3-7 days), no imputation for data missing due to participation in EP0118 will be performed. Subjects will be assigned the same dose in EP0118 as that assigned in EP0085 for the two weeks prior to the start of EP0118. As such, time during the EP0118 study will not be subtracted from the exposure calculations (eg, exposure will be from the start of BRV treatment in the EP0085 study until the date of last dose of BRV in EP0085).

For the calculation of variables related to seizure frequency, the dates during participation in EP0118 will be considered as not done for the purpose of efficacy analyses for EP0085 according to the Seizure Count form entry (eg, these dates will not be considered as days evaluated for seizure frequency).

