##### **8.1.1        28-day adjusted seizure frequency**

The 28-Day Adjusted Partial Seizure Frequency (28DPSF) will be calculated by dividing the number of partial seizures by the number of days for which the DRC was completed and multiplying by 28, eg, as following equation:

$$28DPSF = \frac{\text{Number of partial seizures}}{\text{Number of days completed in the DRC}} \times 28$$

For the 28-day adjusted frequency of all seizure types (partial, generalized and unclassified epileptic seizure), the number of numerator will include partial, generalized and unclassified epileptic seizure.

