### 8.1.3 Responder rate of 28DPSF

A responder is defined as a subject with a  $\geq 50\%$  reduction of 28DPSF from the Baseline to the designated period.

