### 8.1.4 Seizure freedom (partial, all epileptic seizure)

A subject is defined as seizure free for a designated period during the Evaluation Period if they meet **all of** the following criteria:

- Criteria 1: the subject completed the designated period during the Evaluation Period
- Criteria 2: the subject has at least 90% non-missing diary days during the period of time
- Criteria 3: the subject did not report any seizures during the period

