### **8.2.3 Analysis for responder rate of 28DPSF**

The number and percentage of responders will be summarized by study group. The analysis time intervals will be 3-month periods over the Evaluation Period. The denominator of percentage will be based on the total number of subjects with at least 1 seizure assessment during the time interval. The numerator will be the number of responders.

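### One completed diary day is enough to enter a 90-day efficacy interval, so sparse diaries among subjects who stay on treatment can turn unchanged subjects into apparent 100% responders

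*SAP*

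**What the plan says.** SAP 3.2.6 sets two joint conditions for a subject to be analysed in a 3-month efficacy interval. One concerns the diary: "the seizure diary was completed for at least 1 day during the 3-month interval over the Evaluation Period". The other concerns dosing: the last Evaluation Period dose must fall on the interval's final day or later. Intervals are 90 days long, because "a month is defined as 30 days and time intervals based on monthly durations are defined as a multiple of 30 days".

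Within the interval, SAP 8.1.1 obtains the 28-day adjusted partial seizure frequency (28DPSF) by "dividing the number of partial seizures by the number of days for which the DRC was completed and multiplying by 28". SAP 4.1 adds: "Days with missing information will be ignored in the calculation of the seizure frequency". SAP 8.1.3 calls a subject a responder on at least a 50% "reduction of 28DPSF from the Baseline to the designated period". On who is counted, SAP 8.2.3 says: "The denominator of percentage will be based on the total number of subjects with at least 1 seizure assessment during the time interval". The summaries in 8.2.1 to 8.2.3 are unweighted.

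The only diary-completeness threshold is in SAP 8.1.4, for seizure freedom: "the subject has at least 90% non-missing diary days during the period of time". Nothing similar applies to seizure frequency, percent reduction or responder status, and no sensitivity analysis on diary coverage is planned.

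**The concern.** A frequency from one or a few days is a very noisy estimate of a 90-day rate, yet it enters the tables with the same weight as one from a full diary. Most single days carry no seizure, so a one-day diary usually gives a frequency of zero, a 100% reduction and responder status. When a seizure does fall on that day, the frequency becomes 28 per 28 days and the percent reduction is hugely negative.

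The same SAP bars such a subject from being called seizure free over the interval but accepts the subject as a complete responder. The documents do not explain the difference. What is at stake is the 3-month responder and percent-reduction tables, which are how the plan shows the secondary objective, maintenance of efficacy over time.

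**Working it through.** The plan gives no figure for diary completeness or expected response, so there is nothing of its own to reproduce.

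**Inputs from the documents**
- Interval: 3 × 30 = 90 days. Minimum: 1 completed day, or 1/90 = 1.1%.
- Baseline for direct enrollers: 1 to 7 partial seizures in 8 weeks (Protocol 6.1.3, criterion 10), over a fixed 56 days (SAP 8.1.2). That is 0.5 to 3.5 per 28 days.
- Seizure-freedom rule: 0.9 × 90 = 81 days.

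**Assumptions**
- Counts are Poisson, the true rate equals the baseline rate (no change), and completed days are representative.
- The share of subjects with sparse diaries is not documented, so it is varied.
- The card is completed daily, as the footnotes to Protocol Tables 5-1 and 5-2 say.

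**Single subject.** With *b* seizures per 56 days and *d* completed days, the expected count is *m* = *b·d*/56. Then P(apparent 100% reduction) = exp(−*m*), and P(responder by chance) = P(X ≤ floor(0.5·*m*)).

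One completed day: exp(−1/56) = 98%, exp(−4/56) = 93%, exp(−7/56) = 88%. Every one of these chance responders shows a 100% reduction.

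Chance-responder probability by number of completed days:

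| Baseline per 8 weeks | 1 day | 7 | 14 | 28 | 81 | 90 |
|---|---|---|---|---|---|---|
| 1 | 98% | 88% | 78% | 61% | 23.5% | 20% |
| 4 | 93% | 61% | 37% | 41% | 7% | 12% |
| 7 | 88% | 42% | 17% | 14% | 6% | 3% |

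Example: at 4 per 8 weeks and 28 days, *m* = 2 and the threshold is 1, so the probability is exp(−2) × (1 + 2) = 41%. The figures do not fall smoothly because counts are whole numbers.

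**One seizure on a single completed day.** 28DPSF = 28. Percent reduction is (0.5 − 28)/0.5 × 100 = −5500% at 1 per 8 weeks and (3.5 − 28)/3.5 × 100 = −700% at 7. Under the assumptions, the expected percent reduction is zero for any number of days; only its spread grows.

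**Direct-enroller group.** Simulation of 4,000 groups of 30, baselines drawn evenly from 1 to 7, no true change, all other diaries full:

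| Share with a one-day diary (assumed) | Responder rate | SD of the group mean percent reduction | Average group median |
|---|---|---|---|
| 0% | 11.4% | about 9 points | 2.6% |
| 5% | 15.4% | 20 | 5.4% |
| 10% | 19.4% | 27 | 8.5% |
| 20% | 27.6% | 41 | 15.2% |

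Check by hand: the one-day probability averaged over baselines 1 to 7 is 93.2%, so at 10% the rate is 0.90 × 11.4% + 0.10 × 93.2% = 19.6%. With 7-day instead of one-day diaries, the rates at 5%, 10% and 20% are 13.8%, 16.4% and 21.8%.

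**Rollover subjects.** Their baseline rates are not in the documents. With 180 subjects and assumed baselines of 8 to 40 per 8 weeks, the responder rate goes from 0.6% to 4.1%, 7.5% and 14.5% at the same three shares.

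**The case against.** The strongest reply is that near-empty diaries should be uncommon. The last-dose condition removes the most natural source, subjects who stop just after an interval opens. Under Protocol 9 the daily record card is discussed at every visit for completeness, and substantial non-compliance may end participation. Time in EP0118 costs a subject only 3 to 7 diary days (SAP 4.1). Efficacy is secondary and descriptive, medians are reported beside means, and frequency and percent reduction are also summarised over the whole Evaluation Period, where one sparse interval contributes few days.

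Most of that stands as an argument about likelihood. It does not supply an analysis rule: card review and possible discontinuation act on conduct and are discretionary. The whole-period summary does not cushion the responder rate, because SAP 8.2.3 names only 3-month periods for it. The median also moves when the sparse share is not small.

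A reader might infer several stronger things that the documents do not support:
- That diaries thin out over the years and so mask waning efficacy. No passage says so, and no completeness data are given.
- That any sparse diary gives mostly 100% reductions. This holds for one or a few days. At 7 seizures per 8 weeks, zero counts are the majority only up to 5 completed days; at 1 per 8 weeks, up to 38.
- That the mean percent reduction is biased upward. Under the model it is not; it becomes unstable.
- That a 5% share of one-day diaries always adds about 4 points. That needs no true change. If 40% of the sparse-diary subjects would be responders on full data (an assumption), the rise cannot exceed 5% × 60% = 3 points.

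**Conclusion.** The point holds. The interval rule, the completed-days denominator and the responder denominator together assign a full-weight responder status on one diary day, and nothing elsewhere in the SAP checks this for subjects who remain on treatment. For direct enrollers, 88% to 98% of unchanged subjects with a one-day diary would be called 100% responders.

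The effect on the tables depends on an unknown share of sparse diaries: from about 11% to about 15%, 19% or 28% at assumed shares of 5%, 10% or 20% with no true change, and less with a real effect. If sparse diaries prove rare, the tables hardly move and the fix costs almost nothing. The conclusion rests on Poisson counts, representative completed days and daily recording. On the last, Protocol 9 has the card filled in on seizure days, while the footnotes to Protocol Tables 5-1 and 5-2 have daily collection. If only seizure-day entries counted as completed, every such diary would give a frequency of at least 28 and the error would run the other way, so these passages should be reconciled.

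**What to change.** In SAP 3.2.6, mirrored in 8.2.1 to 8.2.3:
- Replace the 1-day condition with at least 28 completed diary days in the 90-day interval, one full unit of the 28-day frequency. Keep the last-dose condition.
- Report the distribution of completed days and the number of subjects excluded, per interval and study group.
- Repeat the responder and percent-reduction tables as sensitivity analyses under the SAP's own 90% rule (at least 81 of 90 days) and under the 1-day rule.

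This needs a sentence or two of SAP text and some extra tables, and no new data. Some subject-intervals drop out, and 28 days is a convention. It reduces chance response at low baselines without removing it: 61%, 41% and 14% remain at exactly 28 days for 1, 4 and 7 seizures per 8 weeks, which is why the 90% version should sit beside it. Even a full diary leaves 20% at 1 per 8 weeks, a residue of the low baseline that no diary rule can remove.

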### **3.2.7        Last Value on BRV Treatment**

Last Value for clinical laboratory parameters, vital signs, and ECGs is the last available result obtained after the first dose of BRV and prior to or on the date of last dose of BRV. All scheduled and unscheduled assessments within this time period will be considered. Last Value will be determined separately for each laboratory parameter.

## **3.3        Definition of Baseline values**

Unless otherwise specified, Baseline for all safety and efficacy variables will be based on baseline of the core study.

For rollover subjects, the baseline value for all safety and efficacy variables is defined as the last non-missing data collected prior to the first dose of study medication in the core study (EP0083 or N01358), unless addressed otherwise for a specific type of data. Baseline seizure frequency will be obtained from the core study (EP0083 or N01358).

For direct enrollers in Japan, the baseline value is defined as the last non-missing data collected prior to the first dose of study medication in study EP0085, unless addressed otherwise. For seizure frequency, the baseline is defined as the seizure counts collected from 8 weeks prior to the first BRV administration. This baseline seizure frequency for direct enrollers is consisted of subject's own document (eg, DRC) and the data in DRC for EP0085 between SV and EV.

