^c If no appropriate EEG result (within the last 10 years) is available, the EEG must be scheduled at the SV and the results received before the EV.

^d A neuro-imaging procedure (brain magnetic resonance imaging/brain computerized tomography scan or any other imaging test) should be performed if no report is available within the previous 2 years. If there is not a known history and clinical signs or suspicion of brain tumor, performing a neuro-imaging procedure for the purpose of the study is not mandatory. If the investigator can judge a participant's eligibility by his/her own medical judgement without performing neuro-imaging procedure, it is also acceptable. However, if the etiology of epilepsy is a brain tumor, or the participant has any intracranial structural abnormality as documented by a previous neuro-imaging procedure, the participant needs to have documentation of a neuro-imaging procedure which is no older than 2 years.

^e At the SV and EV (For DE), historical seizure information (including type, frequency, and date) should be checked. Historical seizure information must have been prospectively recorded on a subject's own document (eg, DRC). After the EV, seizure counts are collected on the subject's DRC on a daily basis

^f Laboratory safety assessment will not be performed at MEV. Only liver function tests will be performed at the MEV in Visit 4 (M3) and Visit 6 (M9). Laboratory safety assessment is mandatory at the FV, except if the FV follows an EDV where laboratory results were normal. The result of the calculated creatinine clearance will be provided by the central laboratory.

^g At the SV, a serum pregnancy test will be performed for female subjects with childbearing potential. At all subsequent visits, a urine pregnancy test will be performed

^h Concomitant levetiracetam is permitted for directly enrolled subjects in Japan, but not allowed for subjects transitioning from EP0083 and N01379.

Table 5-2: Schedule of study assessments for subjects directly enrolled into EP0085 in Japan

Assessments	SV	EV	MEV	FEV	YEV	End of Study Visit or EDV	FV
Visit	V0	V1	V2, V4, V6, V8, V10...	V3, V5, V9...	V7, V11...	NA	NA
Month	-	M0	M1, M3, M9, M15, M21...	M2, M6, M18...	M12, M24...	NA	NA
Week	(-2 to -21 days)	W0	W4, W12, W36, W60, W84...	W8, W24, W72...	W48, W96...	NA	NA

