### 8.1.2 Percent reduction of 28-day adjusted partial seizure frequency

Percent reduction of 28DPSF from Baseline is defined as the percentage reduction of 28DPSF for a designated post-baseline period in EP0085 compared with the Baseline 28DPSF in the core study. This variable will be derived as following equation:

$$\text{Percent reduction} = \frac{\text{Baseline 28DPSF} - \text{Post Baseline 28DPSF}}{\text{Baseline 28DPSF}} \times 100$$

For rollover subjects the Baseline seizure will be obtained from EP0083 and N01358 study. For direct enrollers, the Baseline seizure counts will be collected from 8 weeks prior to the first BRV administration (see section 3.3) and the number of days during the Baseline Period will be set as 56 days.

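### Direct-enroller seizure baseline: SAP 3.3 names a diary source that the visit schedule does not issue before entry, and the fixed 56-day denominator counts any known recording gap as seizure-free

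*SAP*

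**What the plan says.** **Source of the counts.** SAP 3.3 says that the baseline seizure frequency of direct enrollers combines the subject's own document with "the data in DRC for EP0085 between SV and EV". The protocol's visit schedule gives a different picture. Table 5-2 leaves card dispensing blank at Screening and marks it first at the Entry Visit, with retrieval only at later visits. Section 8.1 (Screening) lists no card, and Section 8.2 (Entry) does. Footnote e to Table 5-2 states: "After the EV, seizure counts are collected on the subject's DRC on a daily basis". For the time before that, the same footnote requires a seizure history kept prospectively on the subject's own document and checked at both Screening and Entry. Protocol Section 9 differs again: it has a card handed out at every visit except the Unscheduled and Final Visits.

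**Denominator.** SAP 8.1.2 says that "the Baseline seizure counts will be collected from 8 weeks prior to the first BRV administration" and that "the number of days during the Baseline Period will be set as 56 days". The general definition in SAP 8.1.1, which matches Protocol 12.3, obtains the 28-day frequency by "dividing the number of partial seizures by the number of days for which the DRC was completed and multiplying by 28". SAP 4.1 adds: "Days with missing information will be ignored in the calculation of the seizure frequency". Protocol 12.6 says the same. SAP 3.8 records no change from the protocol-defined analyses.

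**The concern.** Two things do not fit together.

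First, the SAP names a data source for the days between Screening and Entry that the visit schedule does not create. A programmer following SAP 3.3 would look for study-card entries in an interval of up to 21 days for which Table 5-2 and Sections 8.1 and 8.2 issue no card.

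Second, the two halves of one percent-reduction formula treat a missing day differently. After baseline, a missing day leaves both numerator and denominator. At baseline it adds nothing to the count but stays in the 56 days, so it is handled as a day without seizures. No passage sets a minimum completeness for the baseline record or says what to do with a known gap. Because the denominator is the same for everyone, the output will not show whether a subject had any gap.

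The variables at stake are percent reduction and responder rate for the direct enrollers. Their baseline counts are small (1 to 7 partial seizures under inclusion criterion 10), and they also feed the All Subjects column defined in SAP 3.6.

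**Working it through.** **Inputs**

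- Baseline window: 8 weeks before the first dose (SAP 3.3 and 8.1.2).
- Screening-to-Entry interval: 2 to 21 days (Protocol 8.1, Table 5-2).
- Responder: at least a 50% reduction (SAP 8.1.3).
- Planned direct enrollers: 30 of 217 (Protocol 12.8).
- Unrecorded baseline days, k: **not given in the documents**. This is an assumption, ranged from 0 to 21, the longest Screening-to-Entry interval.

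**The plan's own figure.** 8 × 7 = 56 days. It reproduces exactly and is the correct denominator when every day is covered.

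**Effect of k unrecorded days.** Assume a constant seizure rate through the window and let R be the true reduction.

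- Computed baseline = true baseline × (56 − k)/56
- Reported reduction = 1 − (1 − R) × 56/(56 − k)
- True reduction needed to be classed as a responder = 1 − 0.5 × (56 − k)/56

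| k | Baseline understated by k/56 | Reported when R = 50% | True reduction needed for responder |
|---|---|---|---|
| 0 | 0% | 50.0% | 50.0% |
| 2 | 3.6% | 48.1% | 51.8% |
| 7 | 12.5% | 42.9% | 56.3% |
| 14 | 25.0% | 33.3% | 62.5% |
| 21 | 37.5% | 20.0% | 68.8% |

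For k = 21: 1 − 0.5 × 56/35 = 1 − 0.80 = 20.0%.

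**One subject.** Four seizures are recorded over 35 covered days.

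- Fixed denominator: 4/56 × 28 = 2.0 per 28 days.
- Covered days: 4/35 × 28 = 3.2 per 28 days.
- With a follow-up frequency of 1.6, the reduction is 1 − 1.6/2.0 = 20% (non-responder) under the first and 1 − 1.6/3.2 = 50% (responder) under the second.

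**Direction.** For R below 100%, the reported reduction is lower than the true one whenever k > 0. If the follow-up frequency is zero, the reported reduction is 100% for any k. The error therefore never favours the drug.

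**Why the denominator must not be days with an entry.** Protocol Section 9 has the card filled in on days when a seizure occurs, and footnote e asks for the type, frequency and date of seizures, not a daily entry. If a record holds only four seizure dates, dividing by days with an entry gives 4/4 × 28 = 28 per 28 days, against 4/56 × 28 = 2. That would inflate the baseline and overstate the reduction.

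**The case against.** The strongest reply is that no bias has been shown. The protocol requires a prospectively kept record, has it checked at both Screening and Entry, and needs the full 8-week count for inclusion criterion 10. A missing study card is not a missing day. If the record is kept as required, 56 is exactly right and the error is zero. Any error that does arise is conservative. The setting also limits the consequence: efficacy is the secondary objective, all summaries are descriptive, and direct enrollers are shown separately. All of this stands.

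A reader might infer three stronger things that the documents do not support:

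- *That no seizure data exist between Screening and Entry.* The subject's own record is a required source for those days, and Section 9 read literally would supply a card as well.
- *That baselines are in fact understated by 37.5% and responders generally lost.* That needs the longest interval and no recording on any of its 21 days, and the documents report no gap at all. Even then, a subject with a true reduction of 68.8% or more is still classed as a responder.
- *That the denominator affects eligibility.* Criterion 10 uses a raw count, which the 56-day rule does not touch.

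The reply does not remove the conflict over the source. Nor does it remove the absence of any rule for a gap that is known: footnote e requires seizure details to be checked, not which days the record covers.

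**Conclusion.** Two defects stand on the text alone. SAP 3.3 relies on a study diary before entry that Table 5-2, its footnote e and Sections 8.1 and 8.2 do not provide, and Section 9 conflicts with that schedule. SAP 8.1.2 departs from the completed-days rule of SAP 8.1.1 and 4.1 and Protocol 12.3 and 12.6, so a baseline day known to be unrecorded is counted as seizure-free.

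The resulting bias is conditional and runs against the drug. It is nil at k = 0 and lowers a true 50% reduction to between 48.1% (k = 2) and 20.0% (k = 21), assuming a constant seizure rate. The value of k is an assumption. The upper end is the worst case for the Screening-to-Entry interval, not an expectation, and a record that started late would add to it. It affects only those of the roughly 30 planned direct enrollers who have gaps and, through them, the All Subjects column (at most 30/217 = 13.8% of planned subjects). The rollover groups are not affected.

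**What to change.** 1. **Reconcile the source.** Make SAP 3.3, Protocol Table 5-2 with footnote e, and Protocol Sections 8.1, 8.2 and 9 agree. Either dispense the card at Screening and retrieve it at Entry, or name the subject's own prospectively kept record as the only source up to the Entry Visit. If enrolment is over, only the second option remains, together with a matching edit to Section 9.
2. **Change the denominator in SAP 8.1.2.** Use 56 minus the days known not to be covered, meaning days before the record starts and documented gaps. State that a blank day within a covered span counts as seizure-free, not missing. Note the rule in SAP 3.8.
3. **Make gaps visible.** List direct enrollers with fewer than 56 covered days, and show the fixed-56 result as a sensitivity summary.

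The cost is SAP wording and a small amount of data review to establish the covered span for about 30 subjects, plus one card issued a visit earlier if the first option is taken. Where coverage cannot be established from the record, 56 stays in use and the listing should say so.
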